[H2g] Individuals high in dispositional optimism, high in comparative optimism, and low in unrealistic optimism have the most favorable profile with respect to health, anxiety and knowledge. In particular, we expect that these individuals exhibit the best health status and lowest risk factor levels, have the lowest predicted risks of having a heart attack or a stroke within 10 years, worry the least about this risk and have the highest CVD risk factor knowledge (see Radcliffe and Klein, 2002).

Test:

- Regress health status, risk factor levels, predicted 10-year personal CVD risks, worry about CVD risk and risk factor knowledge on the degree of dispositional optimism, a binary variable representing comparative optimism and a binary variable representing unrealistic optimism.
- Unrealistic optimism is computed as described in [H2f] following Radcliffe and Klein (2002). Comparative optimism is a binary variable indicating whether an individual stated a lower perceived personal risk than his/her respective perceived base rate.
- Test whether coefficients of dispositional, comparative and unrealistic optimism are consistent with the hypothesis.

[H2h] Dispositional optimists possess more optimistic risk perceptions, but not more optimistically biased risk perceptions. In particular, dispositional optimism is positively correlated with comparative optimism, but uncorrelated with unrealistic optimism (see Radcliffe and Klein, 2002).

Test:

- Measure correlation between dispositional optimism and comparative optimism.
- Measure correlation between dispositional optimism and unrealistic optimism according to definition of Radcliffe and Klein (2002) (see [H2f]).

[H2i] Individuals understand that they can decrease their personal CVD risk by improving their risk factor profile.

Test:

- Compute fraction of respondents who report a personal CVD risk conditional on reducing exposure to risk factors (i.e. smoking, BMI and blood pressure) (section H) smaller than their perceived unconditional personal CVD risk (F_T and D_C). Test whether this fraction is higher for treatment than for control group.
- Regress binary variable indicating a perceived personal CVD risk conditional on reduced exposure to risk factors smaller than the perceived unconditional personal CVD risk on knowledge about CVD risk factors. Test whether individuals with a higher CVD risk factor knowledge are more likely to state a conditional risk smaller than their unconditional risk.

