- Compute difference between perceived unconditional personal CVD risk and perceived conditional personal CVD risk for both control and treatment groups and regress on variables that indicate the respondents' smoking status, BMI and systolic blood pressure level. Test whether higher risk factor levels are associated with a higher difference between perceived unconditional and conditional CVD risks.

Q3: Do beliefs about susceptibility to CVD respond to information on predicted personal CVD risk?

[H3a] Beliefs about personal susceptibility to CVD are updated to incorporate information provided on objective CVD risk predicted from risk factor exposure.

Test:

- We test whether beliefs are updated consistently with Bayes rule such that,
 - posterior_i = $\lambda \cdot predicted_i + (1 \lambda) \cdot prior_i$ where $\lambda \in [0,1]$ is an updating weight representing the individual's willingness to abandon her own prior in favor of the provided risk information. To estimate λ for the 10-year personal CVD risk, we estimate:

$$(posterior_i - prior_i) = \lambda(predicted_i - prior_i) + \varepsilon_i, \qquad (3.1)$$

where the *prior* is perceived personal CVD risks of the information treatment group before being told their predicted risk obtained from Globorisk (D_T), posterior is the equivalent after being told the predicted risk (F_T) and the predicted is the Globorisk prediction of personal CVD risk. This yields an estimate of the extent of updating following the provision of only personal CVD risk information. $\hat{\lambda} = 1$ indicates complete revision of beliefs in which there is 100% reliance on the new information in the prediction and the prior to completely dismissed. $\hat{\lambda} = 0$ indicates no updating of beliefs. $\hat{\lambda} \in (0,1)$ indicates some updating, which can still be consistent with Bayes. For example, the respondent may weigh the new information and the prior in relation to the perceived sample size from which each is obtained.

• To test the response of risk perceptions to the different types of information provided, we estimate regressions of the general form: $p_i = \beta x_i + \gamma I_i + u_i$, where I_i is a dummy variable indicating whether a respondent has been allocated to the information treatment or to the control group and the interpretation of γ varies according to the definition of the dependent variable as follows:

Dependent variable (p)	Effect identified

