Section 2 asks the respondent to report the chance that someone of the same age and gender will have a heart attack or a stroke within ten years. This is interpreted as the respondent's perception of the CVD base rate. Section 3, as well as Sections 5-7, is completed only by respondents in the information treatment group. These sections are described in the next section of this document. In section 4, the respondent is asked to report the chance that she will have a heart attack or a stroke in the next ten years. This is interpreted as the prior belief of personal CVD risk. In Section 8, the respondent is asked to report what her chance of a heart attack or stroke within ten years would be if she were to adopt healthier behaviour, i.e. to quit smoking (if a smoker) and to control blood pressure and weight.

After stating her perceived CVD risk in Sections 2 and 4 (and 6), the respondent is asked how confident she is in her answer on a five-point scale ranging from 1 (not at all confident) to 5 (extremely confident).

Respondents are likely to differ in how certain they are that the stated probability is close to the actual probability of having a heart attack or a stroke. Moreover, in Section 4 (and 6) the participant is asked how worried she is about having a heart attack or a stroke on a five-point scale ranging from 1 (not at all worried) to 5 (extremely worried).

5. Interventions

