Finally, a treatment group respondent will receive information on what the 10-year CVD risk would be for someone of the same age and gender who did not smoke, and had normal blood pressure and BMI. This will be presented as the optimal risk that could be achieved through primary prevention. If the respondent's risk is above the optimal, then they will be told the reason(s) for this - smoking, above a healthy weight or blood pressure reading is above normal. And the respondent will be told how the risk could be reduced – quit smoking, lose weight, get blood pressure down by taking medication, exercising, losing weight, eating less salt and fat. If the respondent's risk is not above the optimal, then they will be congratulated and advised how to keep the risk low.

CVD risk prediction algorithm

We have several reasons for not using the WHO/ISH risk charts to predict 10-year CVD risk, despite their use in PhilPEN. First, there are the methodological weaknesses of these charts identified in Section 2. They appear to produce downwardly biased predictions of CVD risk, which would result in less variation within the treatment group in the information on CVD risk provided. Besides providing inaccurate information and missing much of the variation in actual risk, we would need a much larger sample size in order to identify the effect of the intervention. It would hardly be worthwhile to randomize to a treatment if there is no variation in that treatment for 90% of the treated.

Further, the WHO/ISH charts only allow categorization of individuals into five ranges of CVD risk. They do not provide a point estimate of the CVD risk for each individual. This would have two drawbacks for our study. First, it would further limit the variation in the information we would be able to provide in the intervention. Second, it would not allow us to test the extent to which individuals use the information provided to update their reported estimate of the CVD risk.

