The primary sampling unit (PSU) and the level at which treatment will be randomly allocated is the barangay. The is the lowest administrative unit in the Philippines. There are 849 barangays in Nueva Ecija. Barangays will be randomly drawn for inclusion in the study and randomly allocated to one of the two treatment groups or the control group with probabilities set to achieve the required sizes of the groups.

Within a barangay, interval sampling will be used: starting from a random location, a procedure will be followed to randomly select households moving out from that point. Selected households will be screened to establish whether each includes anyone aged from 40 to 70 inclusive. If so, one such person will be randomly selected as the main survey respondent and the potential subject of the intervention in the treatment group barangays. Further screening will be undertaken to establish whether the selected person is eligible for the study, mainly on the basis of CVD history (see next section). In addition to the main respondent, we will ask the head of household, spouse or other adult to answer questions about the household in general.

9. Inclusion and exclusion criteria

We restrict attention to individuals aged 40 and above because this is one of the criteria for proceeding from risk assessment to risk screening under the PhilPEN protocol. Hence, we know that all respondents

induced to go for a checkup should be given a full screen with tests for blood glucose, urine protein and, if available, blood lipids. By restricting attention to the 40+ age group, we focus on the population in which CVD risks begin to rise steeply and preventive care is most needed. In addition, Globorisk predicts 10-year CVD risk only for individuals aged 40-74. We exclude those older than 70 because comorbidities are likely to rise steeply beyond that age, and because older individuals are likely to be more cognitively challenged in responding to the risk perceptions and risk attitudes questions.

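### The first two H2i tests include respondents with little or nothing to reduce, which dilutes them as measures of understanding that one's own risk can be lowered

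*Combined protocol and SAP*

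**What the plan says.** Section 3.2, [H2i], lists three tests.

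- **Test 1.** "Compute fraction of respondents who report a personal CVD risk conditional on reducing exposure to risk factors" below their unconditional perceived risk. The unconditional figure is the posterior F_T in the information arm and D_C in the control arm. Then: "Test whether this fraction is higher for treatment than for control group".
- **Test 2.** The same binary indicator is regressed on knowledge of CVD risk factors, with a positive association expected.
- **Test 3.** The size of the difference is computed in both arms, with the instruction to "regress on variables that indicate the respondents' smoking status, BMI and systolic blood pressure level".

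No denominator other than respondents is given for tests 1 and 2. Table 1 shows section H completed by both arms. Section 4 describes the question as the respondent's risk if she were to adopt healthier behaviour, that is "to quit smoking (if a smoker) and to control blood pressure and weight"; only the smoking part is conditional. Section 9 sets eligibility by age ("We restrict attention to individuals aged 40 and above", up to 70), disease history and current medication. It does not require a modifiable risk factor.

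Section 5.2 says that information-arm respondents also receive an optimal figure: "10-year CVD risk would be for someone of the same age and gender who did not smoke, and had normal blood pressure and BMI". Table 1 places this step (section G) just before section H. The script then branches: "If the respondent's risk is not above the optimal, then they will be congratulated and advised how to keep the risk low".

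**The concern.** Tests 1 and 2 score a lower section H answer as understanding and any other answer as a lack of it. That works for a smoker, or for someone with raised weight or blood pressure. It works poorly for a non-smoker with normal weight and blood pressure. Their predicted personal and optimal risks coincide, and in the information arm they have just been told so. An unchanged answer from them agrees with the information but counts against the hypothesis.

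The arm contrast in test 1 is therefore a weighted average of two effects, and only one of them is the effect H2i describes. In test 2, better knowledge gives respondents without a factor no clear reason to report a reduction, so their inclusion weakens the knowledge coefficient. Information that improves understanding where there is something to understand could look less effective than it is.

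**Working it through.** **Inputs from the documents.** Table 5 control proportions: 0.31 with systolic BP (SBP) at or above 140, 0.31 with BMI above 25, 0.17 smoking. Means and SDs (Table 5 and Section 10.1): SBP 125.61 with SD 125.61/7 = 17.9; BMI 23.35 with SD 23.35/5 = 4.67. Section 10: ICC 0.1, cluster size 10, autocorrelation 0.6, compliance 0.6. Table 6: 299 information and 1,361 control for binary outcomes.

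**The plan's own figure.** The plan gives no size or power for H2i, so Table 6 is the reference. With d = 0.46/2.27 for mean CVD risk, 2 × (1.96 + 0.84)²/d² × 1.9 × 0.64 rounds up to 47 clusters, or 470 per arm. Then 470/0.36 = 1,306 for control, and 1/(2/470 − 1/1,305.6) = 287 for information. Both match Table 6. For binary outcomes at h = 0.2 the same steps give 48 clusters (1,333 and 293). Table 6's 1,361 and 299 correspond to 49 clusters.

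**Share q with none of the three factors.**

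- Table 5 margins, independence: 0.69 × 0.69 × 0.83 = 0.395. Under any dependence, the bounds are 1 − 0.31 − 0.31 − 0.17 = 0.21 and min(0.69, 0.69, 0.83) = 0.69.
- Section 5.2 does not put numbers on normal blood pressure or BMI. Section 2 lists lower PhilPEN at-risk limits (BP 120/80, BMI 23). Assuming SBP below 120 and a normal distribution, Φ((120 − 125.61)/17.9) = 0.377. With BMI up to 25: 0.377 × 0.69 × 0.83 = 0.22. With BMI below 23, Φ((23 − 23.35)/4.67) = 0.470, and 0.377 × 0.470 × 0.83 = 0.15.

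**Effect on test 1.** Let d1 be the change in the fraction among respondents with a factor and d0 the change among those without. The contrast over all respondents is (1 − q) × d1 + q × d0. Neither d1 nor d0 is in the documents; the values below are assumptions, in percentage points.

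| q | d1 | d0 = 0 | d0 = −20 | d0 = d1 |
|---|---|---|---|---|
| 0.395 | 20 | 12.1 | 4.2 | 20 |
| 0.22 | 20 | 15.6 | 11.2 | 20 |
| 0.15 | 20 | 17.0 | 14.0 | 20 |
| 0.395 | 10 | 6.0 | −1.9 | 10 |
| 0.22 | 10 | 7.8 | 3.4 | 10 |
| 0.15 | 10 | 8.5 | 5.5 | 10 |

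With d0 = 0 the contrast shrinks by the share q. With a 20-point fall, the sign reverses only if d1 is below q/(1 − q) × 20: 13 points at q = 0.395, 5.6 at 0.22 and 3.5 at 0.15.

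**Does restriction cost more than it gains?** Illustration: control fraction 0.60 with a factor and 0.20 without, d1 = 10 points, d0 = 0, two-sided 5%, no gain from a baseline covariate. Power = Φ((Δ − 1.96 × SE0)/SE1), with SE0 from the pooled proportion and SE1 from the two separate ones. Arm sizes are divided by the design effect 1 + (m − 1) × 0.1, where m is 10 for all respondents and 10 × (1 − q) for the subset.

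- q = 0.395, all respondents: design effect 1.9, effective sizes 157 and 716, Δ = 0.06, power about 0.28. Subset: design effect 1.505, effective sizes 120 and 547, Δ = 0.10, power about 0.54.
- q = 0.15, all respondents: power about 0.49. Subset: design effect 1.75, power about 0.62.

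Section H is asked at baseline, before attrition, so actual numbers would be somewhat larger than Table 6's.

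**The case against.** Several points on the other side stand.

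- *The contrast is randomised.* Barangays are allocated at random, so the comparison is unbiased for the all-respondent fraction. A reader might infer that test 1 is biased as an estimate. It is not; the gap lies between that fraction and the understanding H2i sets out to measure.
- *The direction among those without a factor is open.* A reader might infer that correct learning must lower their fraction. Test 1 compares H_T with the respondent's own posterior F_T, and [H3a] allows partial updating. If the prior exceeds the prediction and the updating weight is below 1, F_T stays above the prediction. Section G then repeats that figure as the optimum. A further move towards it gives H_T below F_T and counts as a reduction. So d0 may be negative, nil or positive; if it equals d1, nothing is diluted.
- *An unchanged answer is not the only defensible one.* Section 4 frames the question as adopting healthier behaviour, and Section 5.2 mentions exercise, salt and fat. A knowledgeable respondent with normal readings may still expect some reduction.
- *Other analyses touch the issue.* Test 3 relates the difference to risk factor levels, but it is not an arm comparison. [H3a] compares F_T − H_T with D_C − H_C, but as a mean over everyone. Both add evidence; neither changes the denominator of tests 1 and 2.
- *The questionnaire (Appendix C) is not in the text reviewed.* A skip rule for section H cannot be excluded, though none is described.

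**Conclusion.** The point holds as one of dilution and interpretation. Tests 1 and 2 include respondents for whom the indicator does not measure what H2i describes, and no other listed analysis repairs that. With no effect in this group, the arm contrast shrinks by about 40% on the Table 5 cut-offs, or by about 15% to 22% on the assumed stricter limits. The shares assume independent risk factors and, for the stricter limits, normal distributions. They also rest on survey margins for ages 40 to 69, whereas the trial excludes people with diagnosed diabetes or on antihypertensives, so the true share may differ.

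A reader might go further and infer that effective information would show up as a null or negative result. The documents do not support that. It needs a fall among those without a factor that is large relative to the gain among the others, and the documents give neither response rate. H2i is secondary and its fraction is not among outcomes i to xxi, so this is a low-cost improvement that leaves the principal outcome untouched.

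**What to change.** In Section 3.2, [H2i], make the primary version of tests 1 and 2 the subset whose baseline Globorisk personal risk exceeds their Globorisk optimal risk. State the blood pressure and BMI values that define the optimum, and use those in the intervention script. The inputs are measured at baseline in both arms and, by Section 6, before the risk perceptions module, so the subset is defined by pre-intervention data and the randomised comparison is kept.

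Report the remaining respondents separately and descriptively by arm (section H answer lower than, equal to or higher than the unconditional answer), without scoring one answer as correct. The all-respondent fraction can stay as a supplementary result.

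The cost is a change of wording and a smaller sample for two secondary tests: about 60% to 85% of respondents on the shares above. If the effect were the same in both groups, restriction would lose some precision and gain nothing. If there is no effect in the excluded group, the illustration shows a net gain in power.

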D _T , D _C	Effect of base rate CVD risk information on perceived personal CVD risk.

F_T, D_C	Effect of information base rate + personal CVD risk information on
	perceived personal CVD risk.
H _T , H _C	Effect of base rate + personal + reduced risk factor CVD risk information
	on perceived personal CVD risk if reduced risk factors.
F_T - H_T , D_C - H_C	Effect of information on change in CVD risk if reduced risk factors on
	perception of that change.

- Using the treatment group only, we obtain an alternative estimate of the effect of being informed of predicted personal CVD risk on perceived personal CVD risk by regressing the latter on an indicator of whether it is measured prior to or after receiving personal risk information. That is, a simple before-after comparison: $p_i = x_i \beta + \gamma 1 (p_i = F_{Ti}) + u_i$, $p_i = D_{Ti}$ or F_{Ti} .
- We will run similar regressions to test for updating of confidence about reported risks and worry about CVD risk. See the last point under [H5a] on the relevance of the impact of information on belief confidence.

[H3b] Individuals who are exposed to the information intervention do not simply memorize numbers and percentages they are told in the treatment, but incorporate the information to update beliefs about event likelihoods related to CVD risks.

Test:

• Estimate the correlation between the prior-posterior change in perceived life expectancy and the prior-posterior change in perceived 10-year CVD risk. A negative correlation means that individuals update their life expectancy in a direction consistent with their revision to perceived personal CVD risk. For example, if the perception of CVD risk is raised, then life expectancy is reduced. We will repeat the same exercise for life expectancies conditional on experiencing a heart attack/stroke. As survival probabilities conditional on a CVD event are independent of CVD risk, a coefficient of zero is consistent with Bayesian updating. We use the same beliefs as described in [H3b] to test for updating following the provision of both base rate and personal CVD risks and the provision of only personal CVD risks.

[H3c] Updating of beliefs is heterogeneous with respect to education, predicted CVD risk, confidence about CVD risk estimates and worry about CVD events.

Test:

• Repeat regression (3.1) allowing λ to vary with the stated characteristics.

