[H3d] Updating of beliefs is asymmetrical in response to positive information, i.e. $prior_i > predicted_i$, and negative information i.e. $prior_i < predicted_i$.

Test:

• We run the following regression:

$$\begin{array}{l} (posterior_{i} - prior_{i}) = \lambda_{1i}(predicted_{i} - prior_{i}) \times 1(predicted_{i} \leq prior_{i}) + \lambda_{2i}(predicted_{i} - prior_{i}) \times 1(predicted_{i} > prior_{i}) + \varepsilon_{i} \end{array}$$

and test $\lambda_{1i} = \lambda_{2i}$ against $\lambda_{1i} > \lambda_{2i}$. That is, under the alternative hypothesis, individuals who receive good news respond more than those who receive bad news. Such asymmetric updating is

consistent with the reinforcement of optimism bias. However, in light of Harris and Hahn (2011) and Shah et al. (2016), we cannot infer a mechanism for optimism bias from $\lambda_{1i} > \lambda_{2i}$ alone.

Q4: Do beliefs about susceptibility to CVD affect behavior in relation to lifestyles and the demand for preventive care?

[H4a] Beliefs play an important role in determining health behavior. Individuals are forward-looking and take into account their perceived susceptibility to CVD in deciding on their use of primary prevention and health lifestyles. Further, they use perceptions of the response of CVD risk to risk factors when deciding whether to change health habits such as smoking and diet/exercise.

Test:

- Run regressions of the form, y_i = βx_i + θp̂_i + ε_i, where the dependent variable is an indicator of a) whether the person has attended a health facility for a checkup, including blood pressure measurement and diagnostic tests, b) whether is taking medication for hypertension/diabetes, c) smoking (at all and intensity), d) BMI, e) exercise and possibly others. In one set of regressions, p̂_i will be the predicted value of the perceived personal CVD risk, which will be obtained from of one of the regressions described under [H3a]. That is, in the first stage, perceived personal CVD risk measured after the giving the treatment group information on the base rate and their predicted personal risk is regressed on the treatment group indicator. The IV estimate of θ tells us how behaviour responds to changes in CVD risk perceptions induced by information on those risks.

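### Equation (3.1) assumes the linear updating rule that H3a says it tests, so some responses that ignore the prediction give a λ between 0 and 1

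*Combined protocol and SAP*

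**What the plan says.** All of this is in section 3.2 of the combined protocol and SAP, under the question whether beliefs respond to information on personal risk.

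- **H3a, purpose.** "We test whether beliefs are updated consistently with Bayes rule such that" posterior = λ·predicted + (1 − λ)·prior, with λ in [0,1]. Here λ "is an updating weight representing the individual's willingness to abandon her own prior in favor of the provided risk information".
- **H3a, estimation.** Equation (3.1) regresses (posterior − prior) on (predicted − prior), with one coefficient and no constant.
- **H3a, reading.** An estimate of 1 means complete revision and 0 "indicates no updating of beliefs". A value between them "indicates some updating, which can still be consistent with Bayes".
- **H3a, other regressions.** Treatment-control and before-after comparisons estimate mean differences in perceived risk.
- **H3b.** Changes in life expectancy are correlated with changes in perceived CVD risk. For life expectancy conditional on an event, "a coefficient of zero is consistent with Bayesian updating".
- **H3c.** "Repeat regression (3.1) allowing λ to vary with the stated characteristics".
- **H3d.** (3.1) is split into λ1 (prediction at or below the prior) and λ2 (prediction above it), again without an intercept. The alternative λ1 > λ2 means that "individuals who receive good news respond more than those who receive bad news".

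**The concern.** A test of a rule needs a wider model in which the rule can fail. Equation (3.1) contains only the rule, so the zero intercept and the unit sum of weights are imposed and never examined. A respondent who ignores the prediction but changes the answer for another reason still contributes to λ, because the prior appears on both sides of the equation.

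This matters for interpretation. Section 3.1 makes the responsiveness of beliefs to information a central question and says that the study can answer it. Respondents in the information arm are asked for their own risk twice in one interview (section 5.2), so a general shift in answers is a plausible rival to use of the prediction. A λ between 0 and 1 does not separate the two.

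**Working it through.** The plan states no figure on this point. The check is algebra plus an illustration.

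**Inputs**
- Mean predicted risk 11.35 and SD one fifth of that, 11.35/5 = 2.27 (section 10.1). The plan itself cautions that this SD does not come from Globorisk.
- Prior: mean 25, SD 20, independent of the prediction. This is assumed; the documents give no distribution of priors. Prior means of 15 to 40 were also tried.
- Answers are counts out of 100 dots (section 4), so they lie in 0 to 100.

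**Estimator.** Let g = predicted − prior and d = posterior − prior. Least squares through the origin gives λ̂ = Σgd / Σg².

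**Uniform drop of s points, prediction ignored.** Here d = −s, so λ̂ = s·mean(prior − predicted) / mean[(prior − predicted)²].

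*Without bounds:*
- Mean difference = 25 − 11.35 = 13.65
- Mean square = 13.65² + 20² + 2.27² = 186.3 + 400 + 5.2 = 591.5
- s = 5: 5 × 13.65 / 591.5 = 0.12
- s = 10: 10 × 13.65 / 591.5 = 0.23

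These figures are not usable as they stand, because a normal prior with mean 25 and SD 20 puts 10.5% of priors below zero.

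*With impossible priors dropped:*
- Truncating at 0 gives the ratio φ(1.25)/Φ(1.25) = 0.1826/0.8944 = 0.204
- Mean prior = 25 + 20 × 0.204 = 29.1
- Variance = 400 × (1 − 1.25 × 0.204 − 0.204²) = 281
- Mean difference = 29.1 − 11.35 = 17.7
- Mean square = 17.7² + 281 + 5 ≈ 600
- s = 5: 5 × 17.7 / 600 = 0.15
- s = 10: 10 × 17.7 / 600 = 0.30

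Simulation with posteriors also floored at 0 agrees: 0.15 and 0.30. For prior means of 15 to 40 the ranges are 0.12–0.17 and 0.24–0.34.

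**Free regression on the same data.** Fit posterior = a + b1·predicted + b2·prior. Without the floor, posterior = prior − s gives a = −s, b1 = 0, b2 = 1 exactly. With the floor, b1 stays at about 0.

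**Other responses that ignore the prediction.** These were simulated at n = 299 (Table 6, binary-outcomes column) with bounded answers, reporting noise of SD 5 (assumed) and three assumed settings for the spread of priors and predictions:

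| Response | λ̂ from (3.1) | Free b1 |
|---|---|---|
| Lower the answer by 8 | 0.21–0.26 | about 0 |
| Report 0.6 × prior | 0.40–0.52 | about 0 |
| Move half-way to 25 | 0.20–0.32 | about 0 |
| Everyone says 20 | 0.51–0.77 | about 0 |

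In all four the 95% interval for λ lay inside (0,1) in every replicate. The joint test of a = 0 and b1 + b2 = 1 rejected in every replicate. It rejected in 6–9% when a λ = 0.5 rule applied to the reported prior was true. Barangay clustering was ignored.

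**H3d under a uniform drop.** With d = −s, λ1 = s·Σ|g|/Σg² over the good-news branch, which is positive, and λ2 = −s·Σg/Σg² over the bad-news branch, which is negative. So λ1 > λ2 by construction. In the unbounded setting above, s = 5 gives 0.16 and −0.25, and s = 10 gives 0.31 and −0.50.

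**The case against.** **The plan claims less than a finding of Bayesian behaviour.** H3a hypothesises that information is incorporated, and calls the result of (3.1) an estimate of how far beliefs move. A reader might infer that the plan would report non-Bayesian responses as Bayesian. The documents do not support that, since an intermediate λ only "indicates some updating, which can still be consistent with Bayes". This stands, and it leaves the opening claim to test Bayes rule as the part that (3.1) cannot deliver.

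**Some departures would show.** A reader might infer that no planned output could reveal a failure. That is too strong. In the same simulations an overshoot with true λ of 1.3 gave 1.17–1.23, and a 5-point rise gave −0.11 to −0.13, all outside [0,1]. H3d would also expose a uniform drop: with bounded answers and n = 299, the 95% interval for λ2 lay wholly below zero in 1,000 of 1,000 simulations for drops of 5 and 10. But the comparison that H3d specifies would label this a stronger response to good news. The plan's caveat there concerns the mechanism behind optimism bias, not an omitted intercept.

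**No treatment effect depends on λ.** The first stage in H4a and the reduced form in H5a use the arm indicator, and belief updating is not the principal outcome. This stands and limits the consequence.

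**A pass/fail test would bring its own error.** Noise in the reported prior also breaks the restrictions. Under a true λ = 0.5 rule the joint test rejected in 22% of simulations at noise SD 5 and 94% at SD 10 in one assumed setting, and in 14–50% and 40–77% in three others. The free b1 stayed near 0.5. So the test can serve as a diagnostic but not as a condition for reporting λ.

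**Conclusion.** The concern holds as a point of specification. Equation (3.1) assumes the zero intercept and the unit sum of weights, and H3b, H3c, H3d and the mean comparisons do not free them. A λ between 0 and 1 is therefore not evidence that respondents used the prediction. In the illustration a 5- or 10-point drop that ignores it gives λ of about 0.15 or 0.30, against a free coefficient of about 0, and H3d turns the same drop into an asymmetry.

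The algebra needs no assumption about the data. The sizes do: the prior distribution, its independence from the prediction and the response rules are all assumed. Nothing in the documents shows that respondents will answer in these ways. Equation (3.1) remains a usable summary of the average weight if the linear rule is accepted.

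**What to change.** 1. Beside (3.1), report posterior = a + b1·predicted + b2·prior for the information arm. Read b1 as the weight on the information.
2. Report the joint test of a = 0 and b1 + b2 = 1 as a diagnostic, noting that noise in the reported prior can also make it reject. Do not make the reporting of λ depend on it.
3. Add an intercept to the H3c and H3d versions. This removes a uniform shift exactly only where answers are free to move. Respondents near 0 cannot drop by the full amount, so results should be read with the share of answers at the floor in view.
4. Reword H3a so that (3.1) estimates an updating weight under an assumed linear rule and is not called a test of Bayes rule.

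The cost is SAP wording and a few extra regressions on data already to be collected. Sample size and fieldwork do not change.
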